**An Intervention to Improve Decision Role Concordance
amongst Newly Diagnosed Breast Cancer Patients**

Study Protocol and Statistical Analysis Plan

The University of Utah IRB #:

00081898

May 17, 2016

Project Summary: Role concordance among patients and providers during the decision making process can impact outcomes, but there is a lack of interventional studies in the literature aimed at improving role concordance during treatment decision making for breast cancer patients. The proposed design is a mixed methods, interventional study with concurrent controls to examine the effects of an intervention to improve role concordance on decisional outcomes and breast cancer specific quality of life among newly diagnosed breast cancer patients.

Project Description:

Rationale: This study is innovative because it is an interventional study aimed at improving role concordance in the treatment decision making process for newly diagnosed breast cancer patients. There are currently no standards of care for patient centeredness in clinical decision making. This project will provide a foundation for a research program that will change this, focusing on treatment decision making in breast cancer patients.

Overview: The proposed design is a mixed methods, interventional study with concurrent controls to examine the effects of an intervention to improve role concordance on decisional outcomes among newly diagnosed breast cancer patients. Providers will be blind to the patient's preferred decision making role in the first half of the study and then informed of the preferred role in the second half of the study. The intervention will be a short conversation that providers will have with patients at the beginning of the clinic visit where the provider identifies the patient's preferred role and their desire to help the patient achieve it. Quantitative comparisons before and after implementation of the intervention and qualitative analyses of the recorded clinical encounters will be performed to evaluate the effects of the provider directed behavioral intervention to improve role concordance. This study design was chosen because once the intervention is introduced providers may have difficulty omitting this behavior from the clinical encounter and this could confound our results. If patient-level randomization was used, providers would need much more oversight and coaching in order to not "forget" which patient is in which arm and the study effects may be biased toward the null. In this small study, if provider-level randomization was used, this could significantly bias assessments of patient involvement due to inherent differences in how the providers approach clinical interactions at baseline. Also, we do not anticipate substantial variability in the pre and post populations during the short time period of the study other than the date of their consultation and, thus, we expect that the populations will be very similar in other characteristics. We plan to examine differences between pre and post-intervention patients to evaluate this.

Objectives:

1. Investigate the impact of a brief provider-led intervention about the patients' preferred role in treatment decision making on role concordance. **We hypothesize that:**
 - a. Role concordance will be improved when the preferred role is discussed with the patient at the beginning of the encounter.
 - b. The provider's perception of the role achieved will be more concordant with the patient's perception when the preferred role is discussed.
2. Investigate the impact of role concordance in the treatment decision making process on short term and long term quality of life and decision outcomes. **We hypothesize that:**
 - a. Patients who achieve role concordance will be more satisfied with the decision process.
 - b. Patients who achieve role concordance will have better QOL and less decision regret at early (2 to 6 weeks) and later (6 months) timepoints after the clinic visit.
 - c. Patients who achieve concordance will be more likely to complete or plan to complete recommended treatments.

Study Subjects: The study population will be newly diagnosed female breast cancer patients scheduled to see one of four breast surgeons at the Huntsman Cancer Hospital Breast Surgery Clinic at the University of Utah. We will exclude patients who have had breast cancer previously, cannot read or write, or have a primary language other than English.

Recruitment: All newly diagnosed patients scheduled in our clinic will be given a recruitment letter as part of their new patient materials (sent the day they scheduled their appointment). They will then be called the day before their visit to gauge interest in participation. If they express interest, they will be sent a consent form electronically so that they can familiarize themselves with the study. They will be asked to arrive at least 30 minutes early for their scheduled appointment (most patients do this anyway) and will be met by a research assistant who will explain the study again and obtain written consent. This same assistant will administer the study scales before and after the clinic visit. Providers will not consent patients nor administer any patient assessments for the study because they will also be delivering the intervention. We expect to enroll a total of 100 patients with 50 in the first year and 50 in the second. We see over 400 new breast cancer patients per year and therefore need approximately 12% of these patients per year to participate in order to reach our recruitment goals. Prior studies using similar methods have had excellent enrollment rates with 98% of eligible patients interested in enrollment.

Methodology: The Patient Preference Scale is the initial scale used in the study and identifies 5 different roles in decision making (Fig. 1). Following completion of the consent process, participants will be asked just prior to the first clinic visit with the surgeon to identify their most preferred role for treatment decision making during that encounter. This will be designated as the preferred role for evaluation of role concordance. For the first 50 patients, the providers will be blinded to the preferred role. After the clinic visit, the participants will complete the Patient Perception Scale which measures patients' perception of the achieved role in the treatment decision making process. After the clinic visit, providers will also complete the Provider Perception Scale which measures the provider's perception of the role achieved by the patient. These three scales are shown in Table 1. The Patient Perception Scale and the Provider Perception Scale will be compared to evaluate the degree of patient-provider concordance between achieved roles. Analysis will also be performed to establish the proportion of patients with perfect role concordance between their preferred and achieved roles. The degree of discordance can also be measured by comparing the number of roles between the preferred role and the achieved role on the 5-point Likert-type scales

Table 1.

Patient Preference Scale (prior to clinic visit)	Patient Perception Scale (after clinic visit)	Provider Perception Scale (after clinic visit)
I prefer to make the final selection about which treatment I will receive	I made the final decision about which treatment I would receive.	The patient made the final decision about which treatment she would receive.
I prefer to make the final selection of my treatment after seriously considering my doctor's opinion.	I made the final selection of my treatment after seriously considering my doctor's opinion	The patient made the final decision about which treatment she would receive after seriously considering my opinion.
I prefer that my doctor and I share responsibility for deciding which treatment is best for me.	My doctor and I shared responsibility for deciding which treatment was best	I shared responsibility with the patient for making the final decision about

	for me.	treatment she would receive.
I prefer that my doctor make the final decision about which treatment will be used but seriously consider my opinion.	My doctor made the final decision about which treatment would be used but seriously considered my opinion.	I made the final decision about which treatment the patient would receive after seriously considering the patient's opinion.
I prefer to leave all decisions regarding my treatment to my doctor.	My doctor made all the decisions regarding my treatment.	I made the final decision about which treatment the patient would receive.

Recording of clinical consultations has been well-studied as a tool for determining patient-centered communication [1-3]. Therefore, all clinic encounters will be digitally recorded, transcribed, and analyzed using the OPTION scale for patient involvement, which is described below. The transcriptions will be de-identified and coded by independent raters (paid graduate students).

Assessments of QOL and decision regret will be performed at early (2 to 6 weeks) and later (6 months) timepoints after the clinic visit. These scales will be distributed electronically and patients will receive a phone call from the study coordinator to remind them to complete the measures. If they have not completed the measures by one week from the reminder phone call, a second call will be placed with an offer to complete the surveys over the phone with the study coordinator.

Chart review of all participants will be reviewed at the 6 month time point to assess for decisions ultimately made and completion or intention to complete recommended therapies. This timeframe was selected because the majority of patients will have completed their surgery, chemotherapy (if needed), and radiation (if needed) or at least have the initiation of these therapies planned. Radiation is always given last and this therapy is the most likely to still be in the planning stages. Also at this time point, endocrine therapy will have been initiated by some patients and may be planned by others.

Intervention: The intervention will take place in the second half of the study, where the research assistant will inform the provider of the patient's preferred role based on the Patient Preference Scale prior to the clinic visit. The provider will then have a brief conversation at the beginning of the clinic visit where they state "I see that you prefer to have treatment decisions made (*together, by yourself, by me*) today. I appreciate knowing this information." The rest of the encounter will proceed as per the provider's usual practice. All other study procedures will be the same and the same perception scales will be used after the clinic visit and concordance and discordance will be examined as described in the study flow diagram.

Outcomes: The primary outcomes will be role concordance and patient satisfaction with the decision process. Secondary outcomes will be role perception concordance between provider and patient, quality of life at 2 to 6 weeks and 6 months after initial clinic visit, decision regret at 2 to 6 weeks and 6 months after initial clinic visit, and completion or planned completion of recommended therapies at 6 months. These time points were chosen to provide an early assessment of the impact of the intervention and to see if the results are durable after a longer period of time while still allowing us to conclude the study within the funding timeframe. There is evidence that decision regret is stable over time out to 4 years after diagnosis [4]. We will also correlate role

preference and concordance with surgical procedure performed or planned to look for associations between these measures and type of surgery received or planned, controlling for ineligibility for breast conservation.

Risks and Benefits of Participation: Participation is completely voluntary and may be withdrawn at any time. This is a low risk study, but some patients may experience distress from the questions on the surveys. If a patient experiences distress, she will be referred to our in-clinic Licensed Care Social Worker and she will make appropriate referrals to psychiatric care if necessary. There is also a low risk of loss of privacy and patients will be made aware of this. The benefits of participation are greater patient awareness of their own preferences and decisions.

Please see the study flow diagram on the following page.

Record decisions made and intentions
to complete therapy

Data Management: All surveys will be administered electronically (tablets will be used for in clinic surveys) and stored on a secure University server. The surveys will be collected both in person (when the patient is in clinic) and electronically. The surveys will be built into and collected in the Research Subject Registry (RSR) database. Only study personnel will have access to the data and the PI will be responsible for deciding the role and level of access for each person. All digital audio recordings will be stored on a secure, password protected University computer in a locked office at Huntsman Cancer Institute. Again, only study personnel will have access to this data. The digital recordings will be transcribed and de-identified for coding and analysis. The de-identified transcripts will only be available to trained coders, the PI, and study coordinator. The electronic transcriptions will be stored on University based, password protected computers in the secured office area of the PI. Badge access is required to enter the office area during non-business hours. Paper versions will only be used if necessary due to computer outages or significant feasibility issues with the electronic transcripts and will be stored in a locked filing cabinet in the PIs locked office. Again, access will only be given to study personnel.

Statistical Analysis:

We are interested in evaluating whether patients play their desired role in treatment planning, and whether informing providers of patients' preferred roles improves patients' perception of achieving their desired role. Specifically, we will study two groups of patients, a non-intervention control group, where providers are blind to the patient's preferred decision making role and an intervention group where the provider is informed of the patient's preferred role. For this study we plan to enroll 100 patients, where the first 50 will be in the no intervention group and the next 50 will be in the intervention group. We expect the results to provide preliminary data for powering a larger extramural grant.

The primary aim of our study (a) is to evaluate patient perception of whether the patient achieved his/her preferred role in the treatment decision. This aim will be met by estimating perception concordance between baseline and after the clinic visit within the intervention and control groups, and testing for group differences in concordance. A secondary goal (b) will be to similarly estimate concordance of provider's perception of the patient's preferred role versus the patient's perception of the achieved role (where both scales will be measured after the clinic visit). In addition, we also plan to test the following outcomes between groups: c) patient's satisfaction with the decision making process, d) FACT-B assessment of short-term QOL, e) decision regret, f) OPTION assessment of patient involvement and g) completion or intention to complete therapies. Finally, we will compare the patient role concordance estimated in a) with improved short-term and longer-term improvements in: outcomes c)-g). Specific methods corresponding to each analysis objective are described below.

a-b) Concordance measures. The patient and provider perception scales consist of 5 levels ranging from active to passive involvement in treatment decisions. Consistent with other similar studies [5-7], our primary concordance measure will be defined as exact agreement in patient responses between the baseline and post clinic visit. Within each group we will provide concordance rates and the associated 95% confidence interval (CI) using the Wilson Score interval approach. We will also report the weighted Kappa coefficient and its 95% CI. Group differences in concordance will be tested using a chi-squared or Fisher's exact test. As a sensitivity analysis for this assessment, we may adjust for potential confounders in a logistic framework predicting concordance. We will consider the following variables for adjustment if they are associated with the concordance outcome: age, education level, and stage of disease.

c) Patient's satisfaction with the decision making process. Satisfaction with the decision making process will be measured directly after the clinic encounter using a modified version of the Holmes-Rovner Satisfaction with

Decision scale which combines several elements of decisional satisfaction and is designed to measure satisfaction with the decision regardless of prognosis or outcome [5, 8]. It also correlates with decision confidence. It uses a Likert-type ranking of 6 items related to the decision. The modified version will measure the satisfaction with the process of decision making rather than the decision itself. Group satisfaction differences will be assessed using a two-sample two-tailed t-test. We will also use linear regression to consider adjusting for the potential confounders described above (a-b) along with the following treatment related variables: type of surgery received and the sequencing of treatment (chemo first vs. surgery first), surgical complications, recommendation for chemotherapy, and recommendation for radiation treatment in these analyses. We will also compare satisfaction with concordance within groups using t-tests (or regression to adjust for covariates). Finally, we will test whether the relationship between satisfaction and concordance differs across groups using linear regression and testing for significance of a group*concordance interaction.

d) Comparing FACT-B assessment of short-term QOL between the groups. Quality of life will be assessed using the Functional Assessment of Cancer Therapy-Breast (FACT-B) questionnaire. This scale will be used prior to the first consultation to establish a baseline for each patient and will subsequently be used at 2 to 6 weeks and 6 months after initial clinic visit. This questionnaire is a well validated tool for assessing quality of life in breast cancer patients. It measures 27 items in five different areas: physical well-being, social/family well-being, emotional well-being, functional well-being, and additional concerns specific to this patient population. It has been shown to have significant sensitivity for changes in performance status and quality of life [9]. We will compare the FACT-B assessment between the intervention and control groups using a linear mixed effects model framework with an unstructured covariance, adjusting for baseline FACT-B levels. The final time point (6 months) is our main time point of interest, but we will also estimate differences at 2 to 6 weeks. We will consider controlling for the covariates described in c). We will also compare FACT-B with concordance within groups using separate linear mixed effects models for each group. Finally, we will test whether the relationship between satisfaction and concordance differs across groups using linear mixed effects regression and testing for significance of a group*concordance interaction.

e) Decision regret. The decision regret outcome will be measured using the Decision Regret Scale which will also be administered at 2 to 6 weeks and 6 months after initial clinic visit. This scale has been used in modified version to assess for elements specific to breast cancer surgery and was found to have high internal consistency [4]. It is a 5 item scale with items ranked on a 5-point Likert-type scale and added together with higher score indicating more regret. The analysis framework for comparing groups will be similar to d), except that there is no baseline level to control for in the models.

f) OPTION assessment of patient involvement. The outcome of patient involvement at the clinic encounter will be measured using the OPTION scale. This scale was developed to measure the extent to which providers involve patients in decisions. A description of the measures used and timeline is illustrated in Table 2. With this scale, 2 independent raters will use a 12 item list to code and score a clinical consultation. It provides a reliable method for detecting differences between the extent of patient involvement with good inter-rater reliability and inter-rater agreement [10, 11]. Raters will be hired graduate students who will be trained in this method, with each rater coding and scoring the first 10 transcripts followed by comparison of the results using the intraclass correlation coefficient (ICC) and its 95% CI before switching to a single rater per transcript method. These scores will be compared between the intervention and control groups for differences in patient involvement using a two-sample t-test and linear regression to adjust for the covariates described in c). We will also compare patient involvement with concordance within groups using t-tests (or regression to adjust for covariates). Finally, we will test whether the relationship between involvement and concordance differs across groups using linear regression and testing for significance of a group*concordance interaction.

g) *Completion or intention to complete therapies.* Group differences in completion or intention to complete recommended therapies will be assessed at 6 months after the clinic visit through chart review of all participants' charts. Intent will be defined as initiation or scheduled initiation of a recommended treatment. The variables of decision made (i.e. type of surgery or sequence of therapy) and completion or intention to complete recommended therapies will be compared between groups using a chi-squared or Fisher's exact test. We will also use a logistic regression framework to test whether the relationship between concordance with completion differs by group. We will consider adjusting for a few covariates described in c), keeping in mind a minimum of 5-10 events per predictor in our models. [12]

Table 2.

Measure Name	Assesses	Prior to Clinic Visit	Immediately After Clinic Visit	2 to 6 Weeks After Clinic Visit	6 Months After Clinic Visit
Patient Preference Scale	Patient's preferred role in decision making process	X			
Patient Perception Scale	Role the patient perceives they played in decision making process		X		
Provider Perception Scale	Role the provider perceives the patient played in the decision making process		X		
FACT-B	Breast cancer specific health related quality of life	X		X	X
Decision Process Satisfaction Scale	Level of satisfaction patient had with the decision making process		X		
Decision Regret Scale	Regret about decision made			X	X
OPTION Scale	3rd party assessment of patient involvement in decision making (from recorded encounter)		X		

Sample Size Justification

Concordance estimates. A similar study conducted by Bilodeau and Degner estimated 50% agreement between a patient's initial decision-role preference and the role that was achieved [13]. Within each group (n=50), we expect to achieve a confidence interval (CI) width of 29% for an expected concordance of 50%, corresponding to a 95% CI of 36%-64%.

Comparison of intervention versus control concordance. With 50 subjects per group we would have 80% power to detect an absolute increase in concordance of 28% in the intervention versus the control group using a two-sided Fisher's exact test at a 0.05 significance level.

Selected References

1. Hack, T.F., et al., *Behind closed doors: systematic analysis of breast cancer consultation communication and predictors of satisfaction with communication.* Psychooncology, 2010. **19**(6): p. 626-36.
2. Clayton, M.F., et al., *Assessing patient-centered communication in a family practice setting: how do we measure it, and whose opinion matters?* Patient Educ Couns, 2011. **84**(3): p. 294-302.
3. Hack, T.F., et al., *Promoting consultation recording practice in oncology: identification of critical implementation factors and determination of patient benefit.* Psychooncology, 2013. **22**(6): p. 1273-82.
4. Martinez, K.A., et al., *Decision Regret following Treatment for Localized Breast Cancer: Is Regret Stable Over Time?* Med Decis Making, 2015. **35**(4): p. 446-57.
5. Lantz, P.M., et al., *Satisfaction with surgery outcomes and the decision process in a population-based sample of women with breast cancer.* Health Serv Res, 2005. **40**(3): p. 745-67.
6. Janz, N.K., et al., *Patient-physician concordance: preferences, perceptions, and factors influencing the breast cancer surgical decision.* J Clin Oncol, 2004. **22**(15): p. 3091-8.

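### Level 5 means all decisions on the patient scale but only the final decision on the provider scale, which can distort patient-provider agreement in secondary outcome (b)

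*Combined protocol and SAP*

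**What the plan says.** Table 1 in the Methodology section sets out three five-level scales. In the last row, the Patient Preference Scale reads "I prefer to leave all decisions regarding my treatment to my doctor" and the Patient Perception Scale reads "My doctor made all the decisions regarding my treatment". The Provider Perception Scale reads "I made the final decision about which treatment the patient would receive", with no reference to all decisions.

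One row up, the patient's level 4 is "My doctor made the final decision about which treatment would be used but seriously considered my opinion" and the provider's level 4 is "I made the final decision about which treatment the patient would receive after seriously considering the patient's opinion".

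Methodology states the use of the two perception scales: "The Patient Perception Scale and the Provider Perception Scale will be compared to evaluate the degree of patient-provider concordance between achieved roles". The Outcomes paragraph lists this as a secondary outcome, and it bears on hypothesis 1b. Under Statistical Analysis, a-b) Concordance measures, "our primary concordance measure will be defined as exact agreement". That sentence goes on to name patient responses before and after the visit, so it is written for outcome (a). For (b), the plan says it will "similarly estimate concordance of provider's perception of the patient's preferred role versus the patient's perception of the achieved role". Weighted kappa is also reported, with the weights not stated.

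**The concern.** An agreement rate between two raters is interpretable only if each category means the same to both. Here the end category does not. The patient reaches level 5 only if the doctor made every treatment decision. The provider reaches it by having made the last one. The provider's level 5 sentence is also the opening of the provider's level 4 sentence with the consideration clause removed, so it is literally true whenever level 4 is true. The patient's level 5 does not follow from the patient's level 4 in that way.

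At stake is whether a 4-versus-5 split reflects different perceptions or different questions. The plan expects the study to supply preliminary data for powering a larger grant, so a distorted agreement rate could be carried forward.

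**Working it through.** **Item check.** Take four kinds of visit and ask which item fits each party (items from Table 1).

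1. *Both perceive that the doctor made the final decision without weighing the patient's view, but did not make every decision.* The provider's match is 5. The patient has no match: 4 adds that her opinion was seriously considered, and 5 says all decisions. If she picks 4, like perceptions count as disagreement.
2. *The patient perceives that the doctor made all decisions; the provider perceives making only the final one, without weighing her view.* Both pick 5. Unlike perceptions count as agreement.
3. *Both perceive that the doctor made all decisions.* The patient picks 5 and the provider would most naturally pick 5. No harm.
4. *Both perceive a final decision by the doctor after weighing the patient's view.* The patient picks 4. The provider's 4 fits, but the provider's 5 is also literally true. A provider who ticks 5 creates a false disagreement.

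The net change in the agreement rate is false agreements (case 2) minus false disagreements (cases 1 and 4). Its sign is not fixed by the text.

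**Weighted kappa.** On five levels a one-level split earns credit 1 − 1/4 = 0.75 with linear weights, or 1 − 1/16 = 0.94 with quadratic weights. The penalty is softened but not removed.

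**Possible size of the false-disagreement part.** Loss in points = 100 × q × m, where q is the share of visits perceived as the doctor's final decision and m is the share of those coded differently on the two scales. The documents give no distribution across the five roles, so both are assumptions.

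| q | m = 25% | m = 50% | m = 100% |
|---|---|---|---|
| 5% | 1.25 | 2.5 | 5 |
| 10% | 2.5 | 5 | 10 |
| 20% | 5 | 10 | 20 |

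**Group comparison.** The Sample Size Justification gives 80% power for a 28-point increase with 50 per group, using a two-sided Fisher's exact test at 0.05. Taking its expected 50% as the control rate, exact enumeration for 50% versus 78% gives 78.9%, which reproduces the stated figure to within about a point. The plan does not tie this scenario to (b); it is borrowed here only to see how a loss would act.

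| Assumed loss | Rates | Difference | Power |
|---|---|---|---|
| None | 50% vs 78% | 28 | 78.9% |
| 5 points in each group | 45% vs 73% | 28 | 77.4% |
| 15 points in each group | 35% vs 63% | 28 | 76.8% |
| 5% of each rate | 47.5% vs 74.1% | 26.6 | 72.9% |
| 10% of each rate | 45% vs 70.2% | 25.2 | 67.3% |

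If q and m are the same in both groups, the loss is an equal number of points, the difference stays at 28 and power barely moves. Power falls materially only if the loss is proportional to the agreement rate, and nothing in the documents supports that.

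**Primary outcome.** Outcome (a) compares the two patient scales, and both refer to all decisions at level 5. This mismatch does not touch it.

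**The case against.** The strongest reply is that nested wording is the format of the instrument. Level 1 overlaps level 2 in the same literal way on all three scales, and the provider's level 5 simply mirrors the provider's level 1. Respondents choose one of five ordered roles, so an unqualified end item next to a qualified one will usually be read as a contrast. A surgeon who weighed the patient's opinion has an adjacent item that says so. This stands as far as it goes: case 4 may be uncommon, and nesting alone is not the defect. It does not answer the mismatch itself. At levels 1 and 2 the overlap is present on both perception scales; at level 5 the two scales name different things, and no scoring note or provider instruction equates them.

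It is also fair to say that exact agreement for (b) is an inference. The explicit definition concerns patient responses only. But (b) is to be estimated in the same manner as (a), under a shared heading, and no other rule is given.

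A reader might infer that the wording lowers agreement in both groups, shrinks the difference that tests hypothesis 1b and costs power, perhaps down to 73% or 67%. The documents do not support this. The direction is open because of case 2. Both groups use the same scales, so an equal loss leaves the difference intact. The lower power figures need a proportional loss that nothing justifies, and they borrow a scenario the plan does not state for (b).

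**Conclusion.** The point holds in a limited form. Level 5 is not the same category on the two scales compared for secondary outcome (b), so the plan as written can score like perceptions as disagreement and unlike perceptions as agreement at the boundary between levels 4 and 5. The absolute agreement rate and weighted kappa for (b) can be distorted. The size cannot be estimated from the documents; the 1.25 to 20 points above is illustrative, covers one direction only and rests on assumed values of q and m. The comparison for hypothesis 1b is distorted only if the wording effect differs between groups or is proportional to agreement. No loss of power should be claimed, and the primary outcome is not affected by this mismatch. The conclusion assumes exact agreement is the rule for (b).

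**What to change.** If enrolment has not started, reword the provider's level 5 item to mirror the patient's, for example: *I made all the decisions regarding the patient's treatment.* The cost is one item in an electronic survey.

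If enrolment has started, keep the present wording in both phases. The first 50 patients are controls and the next 50 receive the intervention, so a change partway could be confounded with group. Instead, add to (b) a pre-specified agreement analysis with levels 4 and 5 combined on both scales, and report it beside the five-level result. It needs no new data and shows how much of the disagreement sits at that boundary. The downside is a coarser measure.

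In the same edit, state explicitly that exact agreement applies to (b), and give the kappa weights. Statistical Analysis also describes (b) as the provider's perception of the preferred role, whereas Methodology and Table 2 measure the provider's perception of the role achieved. That is a separate inconsistency, and those passages must be reconciled.
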